## **7.10 Monitoring and Safety for Specific Toxicities**

During preclinical testing, issues with increased heart rate and lowering of blood pressure were detected. Therefore, heart rate and blood pressure changes should be monitored carefully. When abnormalities are detected both blood pressure and pulse rate should be captured simultaneously

## **8 GENERAL CONSIDERATIONS**

### **8.1 Basic Principles**

This research will be carried out in accordance with the protocol, the International Council for Harmonisation (ICH), Guideline for Good Clinical Practice: Consolidated Guidance (E6), and applicable regulatory requirements(s) including clinical research guidelines established by the Basic Principles defined in the U.S. 21 CFR Parts 50, 56, and 312 and the principles enunciated in the Declaration of Helsinki (revised version Fortaleza 2013).

### **8.2 Institutional Review Board**

This protocol will be reviewed by an appropriate IRB and study enrollment will not commence until the Board has approved the protocol or a modification thereof. The Board is constituted and operates in accordance with the principles and requirements described in 21 CFR Part 56.

### **8.3 Informed Consent**

Written informed consent will be obtained from each subject prior to performing any baseline study-specific evaluations. The informed consent document is prepared by the Investigator or designee, subject to review and approval by the Sponsor, and forwarded to a qualified IRB for final review and approval. The IRB-approved document must contain, at minimum, the eight basic elements of informed consent. Only the most recently IRB-approved Informed Consent Document must be used to consent prospective study subjects. One copy of the signed and dated informed consent document will be given to the subject and the original retained by the Investigator/site.

### **8.4 Indications for Subject Withdrawal**

Subjects will be free to withdraw at any time for any reason, or they may be withdrawn if necessary, to protect their health and safety or the integrity of the study data.

The final report will include reasons for withdrawals. In the event of an early termination, subjects will undergo the procedures described in Section 6.8.

Subjects who experience emesis may be replaced if the emesis could potentially impact drug absorption and therefore the pharmacokinetic data. Cases of emesis will be evaluated by the Sponsor and Principal Investigator to determine if subject replacement is needed.

## **8.5 Termination of the Study**

The Principal Investigator reserves the right to terminate the study in the interest of subject safety and welfare. The Sponsor reserves the right to terminate the study at any time for administrative reasons.

## **8.6 Documentation**

All documents pertaining to the study, including a copy of the approved protocol, copy of the informed consent document and Health Insurance Portability and Accountability Act (HIPAA) documents, completed CRFs (where applicable), drug accountability and retention records, and other study related documents will be retained in the permanent archives of the study site. These will be available for inspection at any time by the Sponsor or the FDA. Per 21 CFR 312, record retention for this study is required for a period of two years following the date on which this study agent is approved by the FDA for the marketing purposes that were the subject of this investigation; or, if no application is to be filed or if the application is not approved for such indication, until two years following the date on which the entire study is completed, terminated, or discontinued, and the FDA is notified.

Subject records will be kept private except when ordered by law. The following individuals will have access to study subject records: Principal Investigator and designees, study Sponsor, monitors, and auditors, the FDA, other government offices, and the IRB.

## **8.7 Trial Monitoring**

Sponsor personnel (or designees) will be responsible for monitoring the study to ensure compliance with the protocol and GCP. Compliance may be verified by one or more of the following methods: on-site visits, frequent communication with the Investigator, and/or review of CRFs and source documents. The Investigator agrees to permit such monitoring as well as audits or reviews by regulatory authorities and the IRB.

## **8.8 Reimbursement, Indemnity, and Insurance**

Reimbursement, indemnity, and insurance shall be addressed in a separate agreement on terms agreed upon by the parties.

# **9 PHARMACOKINETIC ANALYSIS**

## **9.1 Analytical Methodology**

Plasma samples will be analyzed for TBI-223 and M2 using validated assays. Plasma samples from subjects who receive placebo for TBI-223 will not be analyzed.

## 9.2 Pharmacokinetic Analysis

Pharmacokinetic calculations will be performed using appropriate software, e.g. Phoenix™ WinNonlin® (Version 8.1 or higher, Pharsight Corporation) and/or SAS® (Version 9.4 or higher, SAS Institute Inc.).

Pharmacokinetic parameters will be calculated using non-compartmental analysis. The following pharmacokinetic parameters will be determined as appropriate as detailed below.

AUC Extrap (%)	The percentage of AUC inf based on extrapolation
AUC inf	Area under the concentration-time curve from time-zero extrapolated to infinity; calculated as: $AUC_{inf} = AUC_{last} + \frac{C_{last}}{\lambda_z}$
AUC last	Area under the concentration-time curve from time-zero to the time of the last quantifiable concentration; calculated using the linear trapezoidal rule
AUC tau	Area under the concentration-time curve during the dosing interval
C avg	Average steady-state concentration
C last	The last quantifiable concentration determined directly from individual concentration-time data
CL/F	Apparent total clearance after single administration
CLs/F	Apparent total clearance at steady state
C min	Minimum concentration
C max	Maximum concentration, determined directly from individual concentration-time data
C trough	Trough plasma concentration
R AUC	Accumulation ratio for AUC
R Cmax	Accumulation ratio for C max
T last	Time of the last quantifiable concentration
T max	Time of the maximum concentration
T 1/2	The observed terminal half-life, calculated as: $T_{1/2} = \frac{\ln(2)}{\lambda_z}$

V z /F	Apparent volume of distribution in the terminal phase
$\lambda_z$	The observed terminal rate constant; estimated by linear regression through at least three data points in the terminal phase of the log concentration-time profile

For the non-food-effect cohorts, PK parameters calculated from plasma concentration of TBI-223 and M2 following doses on Days 1 and 14 will include, as appropriate:

- Day 1: AUCtau, Cmax, C24, Cavg, Tmax. Additionally, AUCinf, AUCextrap, CL/F, Vz/F,  $\lambda_z$ , and t1/2 should be included if AUCtau  $\geq$  70% of AUCinf.
- Day 14: AUCtau, Cmax, Cmin, Ctrough (i.e., C0), C24, Cavg, Tmax, CL/F, Vz/F,  $\lambda_z$ , t1/2, RAUC, RCmax

For the food-effect cohorts, PK parameters calculated from plasma concentration of TBI-223 and M2 following doses on Days 1, 4, and 17 will include, as appropriate:

- Day 1: AUCtau, AUCextrap, AUCinf, Cmax, C24, Clast, Tmax, Tlast, CL/F, Vz/F,  $\lambda_z$ , t1/2.
- Day 4: AUCtau, Cmax, C24, Cavg, Tmax. Additionally, AUCinf, AUCextrap, CL/F, Vz/F,  $\lambda_z$ , t1/2 should be included if AUCtau  $\geq$  70% of AUCinf.
- Day 17: AUCtau, Cmax, Cmin, Ctrough (i.e., C0), C24, Cavg, Tmax, CL/F, Vz/F,  $\lambda_z$ , t1/2, RAUC, RCmax

Each parameter will be estimated separately for each participant using plasma concentrations of TBI-223 and, as appropriate M2.

Each day one blood sample will be taken immediately before dosing, to measure Ctrough level and to observe the time that steady state is achieved.

Assessments of food effect will include geometric mean ratios of Cmax and AUCtau between Day 1 (fasted) and Day 4 (fed), as well as graphical displays of the profiles. Model-based approaches and comparisons with results from the single-dose study, TBI-223-CL-001, may also be undertaken.

Both individual-participant and group summary-statistics (n, mean, median, geometric mean, standard deviation, standard error of the mean, coefficient of variation, minimum, maximum) data will be reported. Summary statistics will be presented by gender. All tests will be performed using a 2-sided  $\alpha$ -level of 0.05, and appropriate confidence intervals will be provided.

### 9.3 Statistical Analysis

Statistical analyses will be performed using appropriate software, e.g. PhoenixTM WinNonlin® (Version 8.1 or higher, Pharsight Corporation) and SAS® (Version 9.4 or higher, SAS Institute Inc.).

Pharmacokinetic parameters will be summarized by cohort using descriptive statistics. Summary statistics will also be presented by gender within each cohort.

Dose proportionality will be assessed using a power model approach.

## **11 DRUG SUPPLIES**

Global Alliance for TB Drug Development will supply sufficient a quantity of the study drug, TBI-223 SR1 tablets, TBI-223 IR tablets, and Placebo for TBI-223 IR and SR1 tablets 600 mg. Study drug will be shipped to TKL Research, Inc. pursuant to site standard operating procedures. Upon receipt of the study drug products, the supplies will be inventoried and stored in an environmentally controlled and secure, limited access area. The lot numbers of the drugs along with the expiration dates (where available) will be recorded and copies of the Certificate of Analysis (where available) will be maintained on file. Records will be maintained of the receipt and dispensation of the drugs supplied. At the conclusion of the study, any unused study drug will be

returned to the sponsor or destroyed by the site pursuant to written authorization by the sponsor and applicable federal and state regulations.

## **12 ADMINISTRATIVE ISSUES**

The Investigator is referred to the Investigator Brochure, or information provided during the study initiation visit, information provided by the study monitor, and ICH Guidelines for Good Clinical Practice for information regarding the study drug, details, or general considerations to be followed during the course of this study.

## 13 EVENTS SCHEDULE

**Table 12 Schedule of Assessments (Cohorts 1 and 2)**

	SCREEN	CHECK-IN a	Fasted dosing Day 1 and washout Day 2-3			TREATMENT (14 Days) Day 18-19 Follow-up					CHECK OUT	FOLLOW-UP			EARLY WITHDRAWAL	
			-1	1	2	3	4	5-10	11	12-17		20	21-25	26	33 (+1)	
DAY	-28 to -2	-2														
EVENT																
Informed consent and medical history	X															
Check-in questions		X														
Height, weight	X															
HIV/ hepatitis B, C	X															
Serum pregnancy test b	X	X														
FSH b	X															
Urine drug/alcohol/cotinine screen	X	X														
Safety Labs (hematology, chemistry) c	X		X	X	X	X	X	X c		X c		X		X	X	
Coagulation d	X		X	X		X	X	X d		X d		X		X	X	
Urinalysis e	X		X	X		X	X	X e		X e		X		X		
Physical and neurological exams f	X	X	X	X	X	X	X	X f		X f			X		X	
Vital signs (blood pressure, pulse, temperature, respiration rate, and pulse oximetry) g	X	X		X	X	X	X	X	X	X	X	X	X		X	
Concomitant medication review h			←							→						
Adverse events i			←							→						

Protocol TBI-223 CL-002 Version 1.0

	SCREEN	CHECK-IN a	Fasted dosing Day 1 and washout Day 2-3				TREATMENT (14 Days) Day 18-19 Follow-up				CHECK OUT	FOLLOW-UP			EARLY WITHDRAWAL
			-1	1	2	3	4	5-10	11	12-17		20	21-25	26	33 (+1)
DAY	-28 to -2	-2													
EVENT															
Dose j				X			X	X	X	X					
12-lead safety ECGs k	X	X	X	X			X	X		X	X		X		X
Plasma for predose trough PK l,m				X			X	X	X	X					
Plasma for Postdose PK n				X	X	X	X			X	X	X			

ECG = electrocardiogram; FSH = follicle-stimulating hormone; HIV = human immunodeficiency virus; PK = pharmacokinetic.

- a. Confinement to start at Check-in (evening of Day -2) and continue until 72 hours after dosing on Day 17.
- b. Serum pregnancy test at screening and at check-in for females only. FSH completed for postmenopausal females only.
- c. Blood will be collected for safety labs (hematology and chemistry) at Screening and Day -1 and at 6-7 hours postdose on Days 1, 2, 3, 4, 6, 10, 14, 17, and on Days 20 and 26
- d. Blood for coagulation testing will be collected at Screening and Day -1, and 6-7 hours postdose on Days 1, 3, 4, 6, 10, 14, 17, and on Days 20 and 26.
- e. Urinalysis testing at Screening and Days -1, 1, 3, 4, 6, 10, 14, 17, and on Days 20 and 26.
- f. Neurological exam: Performed at Screening, Day -2 and Day -1 around 6-7 hours postdose and prior to blood collection for safety labs on Days 1, 4, 6, 10, 14, 17, and on Day 26.
- g. Vital signs (blood pressure, heart rate [pulse], temperature, and respiration rate) should be measured at screening, check-in, and while subjects are in confinement. Vital sign measurements should be taken within 90 minutes prior to dosing and within 15 minutes of the remaining defined time points in flowchart at study hours 0, 1, 6, and 12 on Days 1 and 17. Furthermore, vital signs will be taken once daily on Days 1 through Day 20 (6 hours after dosing) and once daily on Days 18 through 26 and at early withdrawal (must be done within 15 minutes before review of medication and collection of adverse experiences). Both blood pressure and heart rate should be captured simultaneously. Blood pressure and heart rate should be measured after subjects are in a seated position for 2 minutes and again after standing for 1 minute, except when they are supine or semi-reclined because of study procedures and/or adverse events, or as deemed necessary by the Investigator.
- h. On Day 33 (+1 day), follow-up questioning on concomitant medications will be completed by a phone call.
- i. Subjects will be monitored for treatment-emergent adverse events to be monitored from the time of dosing and throughout the study via safety assessments, observation and participant reporting. Specific adverse event questions will be posed daily throughout the study until Day 26. The inquiry to collect adverse events using non-leading questions will be performed after all other procedures are conducted for the specified time points. On Day 33 (+1 day), follow-up questioning on adverse events will be completed by a phone call.
- j. TBI-223 SR1 and IR tablets and placebo for TBI-223 will be administered orally followed by approximately 200 mL of water. **Note:** Dosing on Day 1 will be fasted. Dosing on Days 4-17 to occur following a high-fat, high-calorie breakfast to begin 30 minutes prior to dose and to end (last bite taken) within 5 minutes prior to dosing
- k. 12-lead safety ECGs will be printed and reviewed on-site by the Principal Investigator or designee. Triplicate ECGs will be completed at screening, Day -2, Day -1, and on Day 26 or upon early withdrawal. All other time points will be single ECG readings. ECGs may be done within 2 hours prior

Protocol TBI-223 CL-002 Version 1.0

to time of dosing and at 3, 6, 12 and 16 hours postdose on Days 1, 4, 8, 10, 12, 14, 17, and on Days 18 and 20. Another single ECG reading will be performed on the morning of Day 20 before discharge. The predose ECG should be completed within 20 minutes prior to the predose blood draw. If a subject experiences a post-dosing QTcF >500 msec with a change-from-baseline QTcF >60 msec, after repeat testing, additional ECGs should be recorded until normalization or return to baseline

- l. Predose trough blood samples will be drawn on Day 1 and daily starting on Day 4.
- m. Duplicate plasma samples will be generated from all blood pharmacokinetic samples.
- n. Postdose blood plasma samples will be drawn at the following timepoints:
  - Day 1: 0.5, 1, 2, 3, 4, 5, 6, 7, 8, 12, 16, 20, 24, 30, 36, 42, 48, 54, 60, and 72 hours. The 72-hour sample is the predose sample of Day 4.
  - Day 4: 0.5, 1, 2, 3, 4, 5, 6, 7, 8, 12, 16, 20, and 24 hours. The 24-hour sample is the predose sample of Day 5.
  - Day 17: 0.5, 1, 2, 3, 4, 5, 6, 7, 8, 12, 16, 20, 24, 30, 36, 42, 48, 54, 60, and 72 hours

**Table 13 Schedule of Assessments (Cohort 3)**

DAY	SCREEN	CHECK-IN a	TREATMENT							CHECK OUT	FOLLOW-UP			EARLY WITHDRAWAL		
			-2	-1	1	2 - 6	7	8-13	14		17	18-22	23	30 (+1)		
EVENT																
Informed consent and medical history	X															
Check-in questions		X														
Height, weight	X															
HIV/ hepatitis B, C	X															
Serum pregnancy test b	X	X														
FSH b	X															
Urine drug/alcohol/cotinine screen	X	X														
Safety Labs (hematology, chemistry) c	X		X	X	X c		X c	X				X		X		
Coagulation d	X		X	X	X d		X d	X				X		X		
Urinalysis e	X		X	X	X e		X e	X				X				
Physical and neurological exams f	X	X	X	X	X f		Xf	X				X		X		
Vital signs (blood pressure, pulse, temperature, respiration rate, and pulse oximetry) g	X	X		X	X	X	X	X	X	X	X	X		X		
Concomitant medication review h			←-----X-----→													
Adverse events i					←-----X-----→											
Dose j				X	X	X	X	X								
12-lead safety ECGs k	X	X	X	X		X				X		X		X		
Plasma for predose trough PK l,m				X	X	X	X	X								
Plasma for Postdose PK n				X					X	X	X					

ECG = electrocardiogram; FSH = follicle-stimulating hormone; HIV = human immunodeficiency virus; PK = pharmacokinetic.

- a. Confinement to start at Check-in (evening of Day -2) and continue until 24 hours after dosing on Day 14.
- b. Serum pregnancy test at screening and at check-in for females only. FSH completed for postmenopausal females only.
- c. Blood will be collected for safety labs (hematology and chemistry) at Screening and Day -1 and at 6-7 hours postdose on Days 1, 3, 6, 10, 14, and on Day 23.
- d. Blood for coagulation testing will be collected at Screening and Day -1, and 6-7 hours postdose on Days 1, 6, 10, 14, and on Day 23.
- e. Urinalysis testing at Screening and Days -1, 1, 6, 10, 14, and 23.
- f. Neurological exam: Performed at Screening, Day -2 and Day -1 and 6-7 hours postdose and prior to blood collection for safety labs on Days 1, 3, 6, 10, 14, and on Day 23.
- g. Vital signs (blood pressure, heart rate [pulse], temperature, and respiration rate) should be measured at screening, check-in, and while subjects are in confinement. Vital sign measurements should be taken within 90 minutes prior to dosing and within 15 minutes of the remaining defined time points in flowchart at study hours 0, 1, 6, and 12 on Days 1 and 14. Furthermore, vital signs will be taken once daily on Day 2 through Day 14 (6 hours after dosing) and once daily on Days 15 through 23 and at early withdrawal (must be done within 15 minutes before review of medication and collection of adverse experiences). Both blood pressure and heart rate should be captured simultaneously. Blood pressure and heart rate should be measured after subjects are in a seated position for 2 minutes and then again after standing for 1 minute, except when they are supine or semi-reclined because of study procedures and/or adverse events, or as deemed necessary by the Investigator.
- h. On Day 30 (+1 day), follow-up questioning on concomitant medications will be completed by a phone call.
- i. Subjects will be monitored for treatment-emergent adverse events to be monitored from the time of dosing and throughout the study via safety assessments, observation and participant reporting. Specific adverse event questions will be posed daily throughout the study until Day 23. The inquiry to collect adverse events using non-leading questions will be performed after all other procedures are conducted for the specified time points. On Day 30 ( $\pm 1$  day), follow-up questioning on adverse events will be completed by a phone call.
- j. TBI-223 SR1 and IR1 tablets and placebo for TBI-223 will be administered orally followed by approximately 200 mL of water. **Note:** Dosing to occur following a high-fat, high-calorie breakfast to begin 30 minutes prior to dose and to end (last bite taken) within 5 minutes prior to dosing
- k. 12-lead safety ECGs will be printed and reviewed on-site by the Principal Investigator or designee. Triplicate ECGs will be completed at screening, Day -2, Day -1, and on Day 23 or upon early withdrawal. All other time points will be single ECG readings. ECGs may be done within 2 hours prior to time of dosing and at 3, 6, 12, and 16 hours postdose on Days 1, 2, 3, 8, 12. Another single ECG reading will be performed on the morning of Day 17 before discharge. The predose ECG should be completed within 20 minutes prior to the pre-dose blood draw. If a subject experiences a post-dosing QTcF  $>500$  msec with a change-from-baseline QTcF  $>60$  msec, after repeat testing, additional ECGs should be recorded until normalization or return to baseline
- l. Predose trough blood samples will be drawn daily starting on Day 1.
- m. Duplicate plasma samples will be generated from all blood pharmacokinetic samples.
- n. Postdose blood plasma samples will be drawn at the following timepoints:
  - Day 1: 0.5, 1, 2, 3, 4, 5, 6, 7, 8, 12, 16, 20, and 24 hours. The 24-hour sample is the predose sample of Day 2.
  - Day 14-17: 0.5, 1, 2, 3, 4, 5, 6, 7, 8, 12, 16, 20, 24, 30, 36, 42, 48, 54, 60, and 72 hours

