## 6.8 End-of-Study Procedures

On the day of study discharge (Day 23 for non-food-effect cohort and Day 26 for the food-effect cohorts), the following procedures will be conducted:

- Physical and neurological examinations
- Vital signs measurements (blood pressure, pulse, temperature, respirations, and pulse oximetry)
- Clinical laboratory tests (hematology, chemistry, urinalysis)
- Coagulation
- Triplicate 12-lead ECG
- Concomitant medication review
- AE assessment

Subjects will receive a follow up phone call on Day 30 (non-food-effect cohort) or Day 33 (food-effect cohorts) (+1 day).

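### Table 13 footnote a ends Cohort 3 confinement on Day 15, against Day 17 in section 6.4 and elsewhere in Table 13; the section 6.7 sample count is also wrong, and Day 17 labs are an optional addition

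*Protocol*

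**What the plan says.** **Confinement, Cohort 3.** Table 13 footnote a has confinement "continue until 24 hours after dosing on Day 14". Section 6.4 keeps these subjects confined until the Day 17 procedures are complete and starts outpatient visits on Day 18. Table 13 has its check-out column at Day 17. Footnote k places an ECG on the morning of Day 17 before discharge, and footnote n takes PK samples to 72 hours after the Day 14 dose. For Cohorts 1 and 2, whose last dose is on Day 17, Table 12 footnote a has confinement "continue until 72 hours after dosing on Day 17".

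**Blood volumes, Cohort 3.** The section 6.7 text gives 14 predose PK samples (56 mL), 52 postdose PK samples (208 mL), 90.9 mL for clinical laboratory tests and a total of about 274.9 mL. Table 7 has 32 postdose samples (128 mL) and the same total.

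**Laboratory days.**
- Hematology and chemistry, Cohort 3: "at 6-7 hours postdose on Days 1, 3, 6, 10, 14, and on Day 23". Cohorts 1 and 2: "at 6-7 hours postdose on Days 1, 2, 3, 4, 6, 10, 14, 17, and on Days 20 and 26".
- Coagulation, Cohort 3: "6-7 hours postdose on Days 1, 6, 10, 14, and on Day 23". Cohorts 1 and 2 also have Day 20.
- Urinalysis, Cohort 3: "Urinalysis testing at Screening and Days -1, 1, 6, 10, 14, and 23". Cohorts 1 and 2: "Urinalysis testing at Screening and Days -1, 1, 3, 4, 6, 10, 14, 17, and on Days 20 and 26".
- Section 6.8 requires labs on the day of study discharge, which it sets at Day 23 for Cohort 3 and Day 26 for Cohorts 1 and 2.

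**The concern.** Footnote a is operative schedule text, and it conflicts with four other places in the protocol. A site that worked from it would release Cohort 3 subjects on Day 15, with PK sampling still due on Days 15 to 17 and no visit at which to do it. The samples at risk are the late ones after the last dose. They support the terminal-phase parameters planned for Day 14 in section 9.2: the terminal rate constant, half-life and apparent volume of distribution. The parameters read from the 24-hour dosing interval (AUCtau, Cmax, C24 and the accumulation ratios) do not depend on them.

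The section 6.7 text states components that do not add up to its own total.

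The laboratory schedule is a different matter, a design choice that could be improved. Safety is the primary objective and Cohort 3 has the highest dose. A silent laboratory change that first appears after the Day 14 draw would not be seen in scheduled labs until Day 23.

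**Working it through.** **1. Confinement.** The last dose is on Day 14, so 24 hours later is Day 15 and 72 hours later is Day 17. Footnote a therefore differs from section 6.4 by 2 days.

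Footnote n lists 20 samples after the Day 14 dose. Those later than 24 hours are at 30, 36, 42, 48, 54, 60 and 72 hours, which is 7 of 20.
- 9 active subjects: 7 × 9 = 63 draws.
- All 12 subjects: 7 × 12 = 84 draws. Section 9.1 says placebo samples are not analyzed, so 63 is the figure that matters.

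**2. Blood volumes.** Reproducing Table 7:
- Clinical labs and coagulation: 12.5 + 7 × 8.5 + 7 × 2.7 = 12.5 + 59.5 + 18.9 = 90.9 mL.
- PK: 14 × 4 + 32 × 4 = 56 + 128 = 184 mL.
- Total: 90.9 + 184 = 274.9 mL, as stated.

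Counting from footnote n: Day 1 lists 13 postdose samples, one of which (24 hours) is the Day 2 predose sample, leaving 12; Days 14 to 17 list 20; 12 + 20 = 32.

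The section 6.7 text as written: 56 + 208 + 90.9 = 354.9 mL against a stated 274.9 mL. The difference is 80 mL = 20 × 4 mL, exactly the surplus of 52 over 32 samples.

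**3. Laboratory timing, in days after the last dose.**
- Cohorts 1 and 2 (Days 17, 20, 26): 0, 3 and 9. Longest interval: 26 − 20 = 6 days.
- Cohort 3 (Days 14, 23): 0 and 9. Longest interval: 9.0 days if Day 23 is drawn at the same clock time as Day 14. If it is drawn at the dosing clock time, taking 6.5 hours as the midpoint of the Day 14 window, it is 216 − 6.5 = 209.5 hours, or 8.7 days.
- Cohort 3 with a Day 17 draw: 0, 3 and 9. Longest interval: 23 − 17 = 6 days.

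Cost in blood: 8.5 + 2.7 = 11.2 mL per subject (11.2 / 274.9 = 4.1%). Clinical-lab blood becomes 12.5 + 8 × 8.5 + 8 × 2.7 = 12.5 + 68.0 + 21.6 = 102.1 mL, and the total 102.1 + 184 = 286.1 mL. Table 6 accepts 408.2 mL for Cohorts 1 and 2. That figure includes a Day 5 draw that Table 12 footnote c omits; without it the figure is 408.2 − 8.5 = 399.7 mL. The comparison holds either way.

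**The case against.** **Footnote a is a slip that nobody would follow.** The same table contradicts it three times, and section 6.4 is clear. This largely stands. The 63 draws are what would be lost if the footnote were followed alone, not an expected loss. Even then the samples up to 24 hours would remain, so a terminal slope might still be fitted, from a shorter stretch of the curve. Section 6.2.5 mentions PK data through the morning of Day 15, but that concerns the data needed for an escalation decision and does not support a Day 15 discharge.

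**The 52-sample figure is clerical.** Agreed. Table 7, footnote n and the stated total all give the right answer.

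**The laboratory schedule is not an error.** This stands in full. Footnotes c, d and e agree with Table 7, and section 6.8 is met on Day 23. A reader might infer from the comparison with Cohorts 1 and 2 that a required discharge lab was left out, or that labs are the one unexplained exception in otherwise matching schedules. The documents support neither. No rule requires the same schedule in every cohort, and the ECG schedules differ too: Cohorts 1 and 2 have ECGs on the last dosing day and the day after (Days 17 and 18), whereas Table 13 footnote k gives Cohort 3 none on Day 14 or 15. Nor are the labs during dosing simply matched. Both schedules have 5 hematology and chemistry days within the 14-day fed phase by the footnotes. Cohorts 1 and 2 also have labs on the Day 1 fasted dose, which makes 6 dosing days, and Table 6 adds Day 5.

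The gap is also softened by other provisions. The Day 14 draw at 6-7 hours is close to the SR Tmax of 7 hours given in section 1.7, section 6.7 allows extra blood at discretion, and daily vital signs and adverse event questions run to Day 23. Cohort 3 is the last planned cohort, so no planned escalation depends on it.

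**Conclusion.** Two statements are wrong as written. Footnote a of Table 13 is 2 days short of every other statement on Cohort 3 discharge; taken alone it would cut off 7 of 20 samples after the last dose, at worst 63 draws in active subjects. The section 6.7 text overstates the Cohort 3 postdose PK sampling by 20 samples (80 mL). In both cases the correct value is plain from the rest of the protocol, so the practical risk is small. That judgement assumes the site reads footnote a together with section 6.4 and the rest of Table 13.

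The absence of Cohort 3 labs between Day 14 and Day 23 is a reasonable place for a cheap improvement and no more. It breaches no stated rule, and no stopping rule depends on it.

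**What to change.** **Correct in any case (text edits only).**
- Table 13 footnote a: replace 24 hours with 72 hours after the Day 14 dose.
- Section 6.7 text for Cohort 3: 32 postdose PK samples and 128 mL in place of 52 and 208 mL. The 90.9 and 274.9 mL figures then stand.

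**Optional, in the same amendment.** Add hematology, chemistry, coagulation and urinalysis at the Cohort 3 check-out on Day 17, drawn with the 72-hour PK sample. Day 17 is not a dosing day, so the 6-7 hour timing does not apply, as for Day 20 in Table 12.
- Add Day 17 to Table 13 footnotes c, d and e and to the grid.
- Table 7: clinical labs during study 8 samples, 68.0 mL; coagulation 8 samples, 21.6 mL; total 286.1 mL.
- Section 6.7 text: clinical-lab blood 102.1 mL, total 286.1 mL.

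The cost is 11.2 mL of blood, one urinalysis and one laboratory set per subject (11.2 × 12 = 134.4 mL over the cohort), at a check-out and venipuncture that are already scheduled.

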### **6.4 Confinement**

Subjects will be admitted to the research center on Day -2.

Subjects in the food-effect cohorts will remain confined until after completion of the Day 20 procedures and will return for follow-up outpatient visits on Days 21-26.

Subjects will receive a follow up phone call on Day 33 (+1 day).

Subjects in the non-food-effect cohort will remain confined until after completion of the Day 17 procedures and will return for follow-up outpatient visits on Days 18-23.

Subjects will receive a follow up phone call on Day 30 (+1 day).

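### Cohort 3 (3000 mg, the highest dose) has no scheduled ECG for its last two doses, including the Day 14 PK and safety day; adding a Day 14 set is cheap

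*Protocol*

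**What the plan says.** Cohort 3 receives 3000 mg once daily, fed, on Days 1 to 14. Table 13 footnote k sets predose ECGs and readings "at 3, 6, 12, and 16 hours postdose on Days 1, 2, 3, 8, 12". It then adds: "Another single ECG reading will be performed on the morning of Day 17 before discharge". Triplicate ECGs are at screening, Day -2, Day -1, and Day 23 or early withdrawal.

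The other main Cohort 3 assessments do fall on Day 14:

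- PK (footnote n): "Day 14-17: 0.5, 1, 2, 3, 4, 5, 6, 7, 8, 12, 16, 20, 24" and on to 72 h.
- Vital signs (footnote g): "at study hours 0, 1, 6, and 12 on Days 1 and 14".
- Neurological exam (footnote f): "6-7 hours postdose and prior to blood collection for safety labs on Days 1, 3, 6, 10, 14".
- Safety labs and coagulation, 6 to 7 h after the dose, and urinalysis (footnotes c, d and e).

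For Cohorts 1 and 2, Table 12 footnote k sets ECGs "at 3, 6, 12 and 16 hours postdose on Days 1, 4, 8, 10, 12, 14, 17", followed by Days 18 and 20. Day 17 is their last dose and their steady-state PK day.

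**The concern.** QTc prolongation is one of the two toxicities for which Section 1.6 sets up dedicated monitoring. The cohort with the highest dose is the one whose ECG schedule stops before dosing ends, and the protocol gives no reason for the difference from Cohorts 1 and 2.

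ECGs are part of the dose review in Section 3.1. Section 6.2.5 bases the escalation decision on PK up to the morning of Day 15, which for Cohort 3 is the Day 14 profile. That profile would arrive with no ECG from the same day. Cohort 3 is the last planned cohort, so its review guides only additional cohorts, though Sections 3 and 3.1 leave room for those.

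Exposure adds some weight. Section 1.5 reports that a QTcF effect above 10 ms can be excluded up to about 8 µg/mL of TBI-223. Cohort 3's predicted mean steady-state peak in Table 3 is 9.7 µg/mL, the only one of the three above that bound. An effect of that size is therefore not excluded at this dose; it is not predicted either.

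**Working it through.** The protocol states no figure to reproduce here. The check is a count of scheduled ECGs against dosing days.

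**Inputs**

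- Cohort 3 serial ECG days 1, 2, 3, 8, 12, then Day 17 morning (Table 13 footnote k); doses on Days 1 to 14.
- Cohorts 1 and 2 serial ECG days 1, 4, 8, 10, 12, 14, 17 (Table 12 footnote k); fed doses on Days 4 to 17.
- Each set is predose, 3, 6, 12 and 16 h: 5 readings, 4 of them post-dose.
- 12 subjects per cohort, 9 on active drug (Section 3).
- Predicted mean peaks 5.7, 7.9 and 9.7 µg/mL (Table 3); single-analyte bound about 8.14 µg/mL (Section 1.5).

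**Doses without an ECG after the last serial day (Day 12):** Days 13 and 14.

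**Nominal gaps** (16 h reading of one set to the start of the next; days × 24 − 16)

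| Stretch | Hours |
|---|---|
| Cohort 3, Day 3 to 8 | 5×24 − 16 = 104 |
| Cohort 3, Day 8 to 12 | 4×24 − 16 = 80 |
| Cohort 3, Day 12 to 17 | 5×24 − 16 = 104 |
| Cohorts 1–2, Day 4 to 8 (longest on treatment) | 4×24 − 16 = 80 |
| Cohorts 1–2, Day 8 to 10, 10 to 12, 12 to 14 | 2×24 − 16 = 32 each |
| Cohorts 1–2, Day 14 to 17 | 3×24 − 16 = 56 |

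The last Cohort 3 gap splits into 2×24 − 16 = 32 h up to the Day 14 dose and 3×24 = 72 h after it. With a Day 14 set it becomes 32 h (Day 12 to 14) and 3×24 − 16 = 56 h (Day 14 to 17). Moving the Day 12 set to Day 14 instead would leave 6×24 − 16 = 128 h of daily dosing without an ECG.

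**Post-dose ECGs per subject over the 14 fed doses**

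- Cohorts 1 and 2: 6 days × 4 = 24.
- Cohort 3: 5 × 4 = 20, rising to 6 × 4 = 24 with Day 14.
- Cohort 3 from Day 8 on: 2 × 4 = 8, rising to 3 × 4 = 12.

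**Post-dose ECG and PK readings at the same hour on the last-dose day** (shared hours 3, 6, 12, 16; 9 active subjects)

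- Cohorts 1 and 2: 4 × 9 = 36 each.
- Cohort 3: 0, rising to 36. Days 8 and 12 have only predose PK. Cohort 3 does have 4 × 9 = 36 such pairs on Day 1, after the first dose.

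**Predicted mean peak divided by the 8.14 µg/mL bound:** 5.7/8.14 = 0.70; 7.9/8.14 = 0.97; 9.7/8.14 = 1.19.

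**Added readings:** 5 × 12 = 60.

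**The case against.** The case for leaving the schedule alone has real points.

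- **Steady state is already covered.** Days 8 and 12 should be at steady state, and their 3 h and 6 h readings sit close to the Tmax values in Section 1.7 (3 h for IR, 7 h for SR). Doses 13 and 14 should give much the same exposure as dose 12. This stands, and it is why the point is modest.
- **Nothing in the protocol requires an ECG on the PK day.** These are single on-site safety readings, and the protocol states no concentration-QTc analysis. This stands too: pairing with PK is a secondary benefit, and the main gain is safety coverage of the last doses.
- **The exposure is not unexplored, and the bound is not sharp.** Part 1 of the single-dose study had Holter ECGs up to 2600 mg, where the mean peak was 16.2 µg/mL. Cohort 2 sits just under the bound at 0.97, and all three peaks are simulated means. That is fair, but the earlier data do not reassure fully. Mean placebo-corrected QTcF change reached 13.3 ms at 2000 mg, and the primary model's upper 90% limits were already 10.06 and 10.20 ms after 1200 mg.
- **The equal 104 h gap from Day 3 to Day 8 is wholly on daily dosing and is not touched by the fix.** True. The fix does not claim to close it.
- **Cardiac monitoring is named separately, and the investigator may order extra ECGs.** Neither has a Day 13 or 14 schedule in Table 13, so neither can be counted as planned coverage.

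None of these supplies a scheduled ECG for the last two doses.

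**Conclusion.** The omission is confirmed: two of Cohort 3's 14 doses, the last two at the highest planned level, have no scheduled ECG, and the final stretch without one is 104 h. The change is worth making but not critical, because steady state near Tmax is otherwise sampled on Days 8 and 12 and no stated analysis depends on a Day 14 ECG.

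This rests on three assumptions:

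- The ECG days are those in Table 13 footnote k. The columns of the table's ECG row could not be read reliably from the extracted text; that row shows no Day 14 mark either.
- Gaps are nominal, taking the 16 h reading as the last of each set and the Day 17 reading at 72 h after the final dose.
- Steady state by Day 8 is inferred from once-daily dosing; the protocol gives no half-life.

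**What to change.** In Table 13, add Day 14 (predose, 3, 6, 12 and 16 h) to footnote k and to the ECG row, so that the serial days read 1, 2, 3, 8, 12 and 14. Keep Day 12. While editing, check that the ECG row agrees with footnote k on the other days.

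The cost is 5 single ECGs per subject, 60 for the cohort. No visit, stay or blood draw is added. Subjects are in the unit at those hours whichever confinement statement applies: Table 13 footnote a has confinement "continue until 24 hours after dosing on Day 14", while Section 6.4 says "Subjects in the non-food-effect cohort will remain confined until after completion of the Day 17 procedures". Blood is already taken at the same five times on Day 14.
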